- ^g **Vital signs** will be obtained while the participant is in the semi-supine position (after 5 minutes), including pulse rate, systolic and diastolic blood pressure, respiration rate, and temperature. At infusion visits, the vital signs for all participants should be taken within 45 minutes prior to the methylprednisolone infusion. In addition, vital signs should be obtained prior to the study drug or placebo infusion, then every 15 minutes (± 5 minutes) for the first hour; then every 30 minutes (± 10 minutes) until 1 hour after the end of the infusion. At non-infusion visits, the vital signs may be taken at any time during the visit.
- ^h **ECGs (pre- and postdose):** ECG should be performed within 45 minutes prior to the methylprednisolone infusion in all participants and within 60 minutes after completion of the ocrelizumab infusion. From OLE Week 72 onwards, ECG assessment is not mandatory; it should only be performed if clinically indicated.
- ⁱ **Telephone interview:** A structured **telephone interview** will be conducted by site personnel every 4 weeks *between visits* to identify and collect information on any changes in the participant's health status that warrant an unscheduled visit (including new or worsening neurological symptoms).
- ^j **MRI scans:** A brain MRI scan should be performed at the start of OLE phase if not done in the previous 12 weeks. In the OLE phase, brain MRIs should be done once a year. Brain MRI scans should occur within a window of ± 4 weeks of the scheduled visit. Also, brain MRI scans will be obtained in participants withdrawn from the OLE phase (at a withdrawal visit) if not performed during the previous 4 weeks.

- ^k **Antibody titers:** Measurement of antibody titers against common antigens (mumps, rubella, varicella, and *S. pneumoniae*) will be performed.
- ^l **HAHA:** In any case of anaphylaxis, anaphylactoid reaction, or serious or severe hypersensitivity reaction, HAHA and ocrelizumab concentration samples should be collected as close as possible to the event and then at 4 and 16 weeks postdose.
- PK samples:** In any case of anaphylaxis, anaphylactoid reaction, or serious or severe hypersensitivity reaction, HAHA and ocrelizumab concentration samples should be collected as close as possible to the event and then at 4 and 16 weeks postdose.

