Magnetic resonance imaging is a useful tool for monitoring CNS lesions in MS. Different MRI-derived parameters have been related to clinical activity and T1-weighted Gd-enhancing lesions or new and/or enlarging hyperintense T2 lesions have been related to relapses. It is hypothesized that changes in brain volume may reflect brain atrophy as a result of MS-related tissue loss and may thereby correlate with long-term clinical outcome in these participants.

Brain MRI scans will be obtained in all participants at baseline and at Weeks 24, 48, and 120.

Scans will be performed by trained and certified MRI technicians. The following time windows apply:

- Visit 2 (baseline): after screening visit, but at least 10 days prior to the baseline visit
- Visit 5–17 (Weeks 24–120): should be performed within a window of ± 4 weeks of the scheduled visit
- In additional cycles during the blinded treatment period, an MRI should be performed annually
- In the OLE phase, MRI should be performed annually

If participants receive corticosteroids for an MS relapse, every effort should be made to obtain the scan prior to the first steroid dose if the pre-steroid scan is within 1 week of the scheduled visit. In participants receiving corticosteroids for an MS relapse, there should be an interval of 3 weeks between the last dose of corticosteroids and the scan.

The MRI will include the acquisition of scans at each timepoint with and/or without IV administered Gd contrast enhancement.

During the blinded treatment period, **MRI scans will be read by a centralized reading center for efficacy endpoints.** The centralized reading center is blinded to the treatment assignment and the reading is performed in the absence of clinical information. Further details on scanning acquisition sequences, methods, handling and transmission of the scans, certification of site MRI radiologist/technicians, and the procedures for the blinded analysis of the scans at the central reading center are described in a separate MRI technical manual.

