The study has been unblinded at the end of the blinded treatment period in September 2015 (clinical cutoff date [CCOD] 24 July 2015) when reaching at least 120 weeks after the last patient randomized provided that the planned number of confirmed disability progression (CDP) has reached 253, (number of events included in the primary analysis: 256). After the positive readout, patients were given access to the OLE starting from 12 October 2015. In the period between the CCOD for the Primary CSR and OLE initiation, the Sponsor, sites, and patients were sequentially unblinded. This period corresponds to the Extended Controlled treatment period (ECP).

encompasses all efficacy data from the double-blind period (DBP) (previously reported in the Primary CSR) plus any additional efficacy data collected during the controlled treatment period up to the time at which the patient received their first open-label dose of ocrelizumab or until withdrawal.

This document has been updated (Version 5) to describe the further analyses to be performed, on:

1. the ECP, including additional data collected after the primary CCOD up to the entry into OLE.
2. the OLE period, including additional data collected from the first dose of Ocrelizumab in OLE.
3. the combined periods of ECP and OLE.

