- For OLE, demography and stratification factors, baseline disease characteristics, MS disease history and baseline MRI data will be summarized using the information collected at OLE baseline as described in the previous section, but subsetting for the OLE ITT population.
- OLE baseline score (EDSS, MRI, etc.) is the latest score collected prior to (including) OLE 1st Dose and after (including) Week 120. If the patient had no measurements within the defined time window, then set the OLE baseline score to be missing.

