4.5.2.3 Change in Total Volume of T2 Lesions on MRI Scans of the Brain from Baseline to Week 120

For the assessment of differences in the percent change in total volume of T2 lesions from baseline up to Week 120, ranked ANCOVA and MMRM analyses will be undertaken using the same approach as described above in Section 4.5.2.2, except that the baseline covariate for the MMRM will be baseline log-transformed T2 lesion volume, geographical region (U.S. vs. ROW), and age (≤ 45 vs. >45 years).

T2 lesion volumes below the lower limit of quantification of 0.009 cm^3 (3 voxels) will be set to this limit.

Extension Periods

This analysis will be extended to include data collected during the OLE period. Ratio relative to baseline until the last mature visit during the combined ECP+OLE period and ratio relative to OLE baseline until the last mature visit during the OLE period will be analyzed. Note that no additional MRI assessments were performed between 120 weeks and OLE start, hence analysis for the ECP period is the same as that for the DB period.

4.5.2.4 Percent Change on MRI from Week 24 to Week 120 in Total Brain Volume

For the assessment of differences in the mean percentage change in brain volume on MRI scans from Week 24 to Week 120, an MMRM analysis will be undertaken using the same approach as described above in Section 4.5.2.2, except:

- The response variable will be the percentage change from Week 24 to subsequent visits (Weeks 48, and 120). Baseline brain volume data will not be a feature in this analysis.
- Covariates will be brain volume at Week 24, geographical region (U.S. vs. ROW), and age (≤ 45 vs. >45 years).

The choice of Week 24 as “baseline” in this analysis, rather than the baseline visit, is a widely accepted approach to establish a stable baseline and avoid the physiological effect of pseudo-atrophy.

Extension Periods

This analysis will be extended to include data collected during the OLE period. Percentage change from Week 24, baseline and OLE baseline until the last mature visit will be analyzed.

4.5.2.5 Change from Baseline in Quality of Life as Measured by the SF36 (Physical Component)

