5. The study originally planned to enroll approximately 630 patients who were to be followed for at least 120 weeks. The study actually enrolled 732 patients (last patient enrolled on 27 December 2012). To explore the effect of the higher enrollment number, the analysis of the primary efficacy endpoint will be performed using the first 630 patients on the basis of their randomization dates (ITT population) at the time of the primary analysis.
6. The primary analysis described above will be adjusted with additional strata for the baseline presence of gadolinium-enhancing T1 lesions (present or absent) and baseline EDSS (≤ 5.5 vs. > 5.5).
7. PPMS is characterized by a progressive course from disease onset typically without superimposed discrete clinical attacks or relapses (Ebers 2004). The primary analysis on CDP for ≥ 12 weeks, described above will be performed excluding patients who have any clinical relapses during the study. Clinical relapses include protocol-defined relapses.
8. For the time to onset of CDP for ≥ 24 weeks, the influence of early progression events on treatment effect will also be evaluated by omitting the EDSS assessments performed between randomization and the Week 12 visit (≤ 83 days after randomization) with use of the ITT population.
9. For the time to onset of CDP for ≥ 24 weeks, the analysis will be performed excluding patients who have any clinical relapses during the blinded treatment period.

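### The SAP puts no recency limit on the OLE baseline MRI, so a missed or post-dose OLE-start scan can make a Week 120 scan, at least about half a year old, the baseline for OLE-only change

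*SAP*

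**What the plan says.** SAP 4.4 (Extension Periods) defines the OLE baseline for all measures together: "OLE baseline score (EDSS, MRI, etc.) is the latest score collected prior to (including) OLE 1st Dose and after (including) Week 120". It adds: "If the patient had no measurements within the defined time window, then set the OLE baseline score to be missing". SAP 4.5 applies this baseline to all OLE-period efficacy analyses.

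Protocol Table 4, MRI footnote, says: "A brain MRI scan should be performed at the start of OLE phase if not done in the previous 12 weeks". The same footnote continues "Brain MRI scans should occur within a window of" ±4 weeks around the scheduled visit. It does not require the scan to precede the first open-label infusion.

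On scans in the interval, SAP 4.5.2.3 states: "Note that no additional MRI assessments were performed between 120 weeks and OLE start". SAP 4.5.3 repeats this. Protocol 5.11.2 had planned otherwise: "In additional cycles during the blinded treatment period, an MRI should be performed annually".

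The OLE-only MRI outputs that use this baseline (SAP 4.2, 4.5.2.3, 4.5.2.4 and 4.5.3) are ratio or percent change in T2 lesion volume, non-enhancing T1 lesion volume, and total brain, cortical grey and white matter volume.

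**The concern.** The rule suits a measure taken every 12 weeks and again on OLE Day 1. MRI has a long gap after Week 120 and then one scan around OLE start. If that scan is missed, or is done within its permitted window but after the first dose, nothing stops the rule from reaching back to Week 120. The clause that sets the baseline to missing does not act, because the Week 120 scan lies inside the stated window. A late OLE-start scan then becomes a post-baseline value.

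The OLE-only analyses are meant to describe change on open-label ocrelizumab. For the affected patients they would also contain change from before the switch. SAP 2 says patients stayed in their randomized group until they switched, so that added change accrued on placebo in one arm and on ocrelizumab in the other. It need not cancel between arms. The OLE baseline MRI summary in SAP 4.4 would be affected too.

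**Working it through.** **Inputs**
- Last enrolment (SAP 4.5.4, item 5): "last patient enrolled on 27 December 2012", taken here as the randomization date.
- OLE opening (SAP 1): "patients were given access to the OLE starting from 12 October 2015".
- Primary clinical cutoff: 24 July 2015 (SAP 1).
- Cutoff to OLE entry: about 3 months, then about 6 months of gradual switching (SAP 2).
- Anticipated accrual: 12 to 18 months (Protocol 4.1.2). No first-patient date is given.
- Week 120 is Study Day 841 (Protocol Table 1), that is, randomization + 840 days.

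**The plan's own figure.** 24 July 2015 to 12 October 2015 is 80 days, or 80 / 30.44 = 2.6 months. This agrees with the SAP's figure of about 3 months.

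**Gap = first OLE dose date − Week 120 date**

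Shortest gap, from stated dates: 27 Dec 2012 + 840 days = 16 Apr 2015. To 12 Oct 2015 is 179 days = 25.6 weeks = 0.49 year. If the Week 120 scan was done 4 weeks late, the gap is 25.6 − 4 = 21.6 weeks. Both exceed the 12 weeks within which Table 4 accepts an existing scan in place of the OLE-start scan.

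Earliest patients, under assumed accrual, with entry from OLE opening to cutoff + 9 months (24 Apr 2016):

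| Accrual assumed | First randomization | Week 120 | Gap at 12 Oct 2015 | Gap at 24 Apr 2016 |
|---|---|---|---|---|
| 12 months | 27 Dec 2011 | 15 Apr 2014 | 1.49 years | 2.03 years |
| 18 months | 27 Jun 2011 | 14 Oct 2013 | 1.99 years | 2.53 years |

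**Share of the measured interval that precedes OLE** = gap / (gap + OLE time). OLE Week 48 is 336 / 365.25 = 0.92 year.
- Gap 0.49 year: 0.49 / (0.49 + 0.92) = 35%.
- Gap 2.53 years: 2.53 / (2.53 + 0.92) = 73%.

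At OLE Week 96 (1.84 years) the shares are 21% and 58%.

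**Does the fallback depend on how the window is read?** The SAP does not say whether its limits are dates or nominal visits.
- Dates: a post-dose OLE-start scan is excluded. The baseline is the Week 120 scan if that scan was taken on or after the Week 120 date. If it was taken early, as the ±4-week window allows, the baseline is missing.
- Visits: a late scan labelled as the OLE-start visit qualifies. A missed scan still falls back to Week 120.

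Neither reading limits how old the baseline may be.

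**The case against.** The trigger is not shown to have occurred. Table 4 puts the scan in the Week 0 column, and a scan on the day of the first dose qualifies. No document says how many scans came later or were missed. This stands, and it is why no share of patients can be given.

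The reading is unsettled. Under a visit reading the late-scan route closes, and under a strict date reading some baselines become missing instead of old. This also stands. It narrows the set of affected patients without emptying it.

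The SAP knows about the gap. SAP 4.5.3 notes that it varies between patients and specifies change per year between successive scans. The combined-period analyses keep the original baseline and are unaffected. Both points are right, but neither repairs the OLE-only ratio and percent-change outputs. Annualizing corrects for the length of an interval, not for assigning it to the wrong treatment period.

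A post-dose baseline has its own problem. A scan at 4 weeks can follow both Cycle 1 infusions, and SAP 4.5.2.4 uses Week 24 as the brain-volume reference to avoid pseudo-atrophy. This stands and shapes the fix.

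Stronger readings are tempting. A reader might infer that every patient falls back to Week 120, because the SAP reports no MRI before OLE start. Table 4 schedules a scan at OLE start, so the documents do not support that. A reader might also infer that the early-versus-delayed difference is overstated. That needs worse change on placebo during the gap on each volume, and similar rates of late or missed scans in both arms. The documents show neither.

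**Conclusion.** The point holds as a gap in the derivation rule. SAP 4.4 can accept as OLE baseline an MRI much older than the 12 weeks the protocol itself tolerates, and the missing-value clause does not prevent it.

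The lower figure, 25.6 weeks for the last-enrolled patient entering when the OLE opened, follows from dates in the SAP. The upper figure, about 2 to 2.5 years, rests on anticipated accrual and about 6 months of switching, and should be quoted only with those assumptions. Both rest on the SAP's statement that no scans were done after Week 120. If the protocol's annual scans do exist, the fallback scan would be more recent.

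For affected patients, roughly a third to three quarters of the interval measured at OLE Week 48 would precede OLE. The number of such patients is unknown, and the direction of bias is plausible only. The pre-OLE interval was on randomized treatment but not all of it was blinded, since SAP 2 describes gradual unblinding before the switch. The primary analysis and the secondary testing hierarchy are not touched.

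**What to change.** In SAP 4.4, give MRI its own OLE-baseline rule, in order of priority:
1. the latest scan within the 12 weeks before, up to and including the date of, the first OLE dose;
2. if there is none, the earliest scan up to 4 weeks after that dose;
3. otherwise missing, with no fallback to the Week 120 scan.

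The 12-week and 4-week limits are those already in Table 4. Repeat the OLE-only MRI analyses with pre-dose baselines only as a sensitivity check, particularly for brain volume. Report by arm how many patients fall under each step, since the documents leave this open. Keep the current rule for EDSS and the timed tests.

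The cost is a change of wording and of one derivation, with no new data. SAP 2.3 lists the final CSR as planned, so the change can still be made. The downside is that some baselines will be up to 4 weeks post-dose, after first exposure to ocrelizumab in former placebo patients, and a few patients will have none.

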4.5 EFFICACY ANALYSIS

All statistical hypotheses for the primary and secondary endpoints and treatment comparisons will be tested at the 5% significance level ($\alpha=0.05$) against two sided alternatives.

Apart from EDSS, for all other assessments, the baseline value will be used as the last non-missing value on or before the date of the first infusion of study drug. Baseline

EDSS is calculated differently. The derivation of baseline EDSS and time to onset of CDP is discussed in Section 4.5.1.

All primary and secondary efficacy endpoints will be stratified by region and age for analysis. The regional stratifications are U.S. and ROW. The age categories are ≤ 45 years and > 45 years.

Extensions Periods

The analyses of the ECP and the combined ECP+OLE periods will be using the same baseline value as the primary analysis. For the analyses of the OLE period, the OLE baseline score is used.

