- ^a Participants who enroll early will require additional 24-week treatment cycles in the blinded treatment period beginning at Week 120. Participants should complete the assessments outlined above. See [Table 2](#) for the schedule of activities for subsequent additional treatment cycles.
- ^b **Informed Consent** will be obtained in written form from all participants at screening in order to meet eligibility for the study. Participants who exhibit confirmed disability progression with 24-week confirmation will require written re-consent to continue in the blinded treatment period of the study.
- ^c **Vital signs** will be obtained while the participant is in the semi-supine position (after 5 minutes), i.e., pulse rate, systolic and diastolic blood pressure, respiration rate and temperature. On infusion visits, the vital signs should be taken within 45 minutes prior to the methylprednisolone infusion in all participants. In addition, vital signs should be obtained prior to the study drug or placebo infusion, then every 15 minutes (±5 minutes) for the first hour; then every 30 minutes (±10 minutes) until 1 hour after the end of the infusion. On non-infusion days, the vital signs may be taken at any time during the visit.

Table 1 Schedule of Activities: Screening through the End of Treatment Period (cont.)

- ^d After informed consent, but prior to initiation of study medications, only serious adverse events caused by a protocol-mandated intervention will be collected (e.g., serious adverse events related to invasive procedures such as biopsies, medication washout, or no treatment run-in).
- ^e A structured **telephone interview** will be done on a 4-week basis between visits *up to* 48 weeks after the last infusion to identify and collect information on any changes in the participant's health status (including, new or worsening neurological symptoms) that warrant an unscheduled visit.
- ^f **MRI scans:** brain MRI scans should occur within a window of ± 4 weeks of the scheduled visit. Brain MRI scans will also be obtained in participants withdrawn from the treatment period (at a withdrawal visit) if not performed during the previous 4 weeks.

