5.10.1.1 Baseline Visit (Visit 2) for the Blinded Treatment Period

Most assessments for this visit should be completed on Day 1 prior to the start of study treatment (i.e., the first IV infusion of ocrelizumab or placebo). Participants will have their vital signs checked at the specified timepoints before treatment onset and during and after the infusion (see [Section 5.12.1](#)). In addition, these participants will have laboratory samples for PK (see [Section 5.14](#)) and for B cell subtyping (see [Section 5.13.2](#)) taken before and after dosing. The participant should remain in observation for at least 1 hour after the completion of the infusion is administered (see [Section 6.2.1](#)).

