Version 3 (28 January 2015, Protocol Version D)

Updates made at this time include the following substantive changes:

- Change of the baseline definition for assessments other than EDSS to include the baseline/Day 1 visit into the baseline. Blinded review of the data indicated that baseline assessment on Day 1 occurred after the day of randomization in many cases. Thus, restricting the baseline to up to and including the day of randomization would have led to a considerable number of patients without baseline assessments.
- The change in 25-foot timed walk from baseline to Week 120 was added to the subgroup analyses.

Version 4 (03 September 2015, Protocol Version E)

This Statistical Analysis Plan has been updated to align with the amended study protocol (WA25046, Version E, 25 February 2015). Updates made at this time include the following substantive changes. The rationale for the update is to provide full and complete information on these important aspects prior to database lock.

Changes to the statistical analyses methods:

- Experience from the RMS Phase III program and blinded review of WA25046 data indicated that the use of MMRM on the absolute change in 25-foot timed walk from baseline to Week 120 would violate the assumptions of normal distribution of the residuals. Therefore, we will analyze relative change from baseline. The p-value of the non-parametric ranked analysis of covariance (ranked ANCOVA) on the percent

change from baseline will be reported. The LOCF method will be used to impute missing values. Assuming a higher withdrawal rate in the control than in the treatment arm and a monotonous increase in the 25-foot timed walk, this method is expected to be conservative. Since the ranked ANCOVA does not provide estimates of the treatment effects, these will be derived using MMRM analyses on the log-transformed post-baseline/baseline values.

In addition, rules for handling outliers in 25-foot timed walk were added based on the Multiple Sclerosis Functional Composite (MSFC) Manual and published data on reference ranges from healthy subject cohorts.

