4.7.4 Laboratory Data General Laboratory Evaluations

Abnormal laboratory outcomes will be reported. A summary of the number and percentage of patients with abnormal laboratory outcomes, along with each grade by laboratory parameter, will be summarized by treatment group for all laboratory assessments.

The absolute values and changes from baseline at each visit will be summarized for all laboratory assessments.

For the liver laboratory parameters, the number and percentage of patients with an elevated post-baseline AST or ALT level will be summarized by treatment.

CD19

The median CD19 cell count will be displayed graphically over time from the first infusion of study drug. Absolute CD19 counts and percent changes from baseline in the CD19 count will be summarized over time.

Immunoglobulins

The median immunoglobulin levels (IgA, IgG, IgM, and total Ig) will be displayed graphically over time from the first infusion of study drug. Absolute values, changes from baseline, and percent changes from baseline will be summarized over time. At each timepoint, the number and percentage of patients with immunoglobulin levels lower than the lower limit of normal will be presented.

Antibody Titers

If data are available, antibody titers for mumps, rubella, varicella, and *Streptococcus pneumoniae* will be summarized for the number and percentages of patients with a positive level by visit.

Anti-Drug Antibodies

ADAs, also called human anti-human antibodies, will be summarized over the blinded treatment period by treatment group. The baseline prevalence and post-baseline incidence of ADAs will be displayed. The number of patients with treatment-induced ADA will also be displayed. A table that summarizes ocrelizumab serum concentrations ($\mu\text{g/mL}$) at timepoints where ADA samples were collected and analyzed will be presented. A listing by treatment of antiocrelizumab antibody data will be presented for patients with at least one ADA sample.

HBV DNA

HBV DNA in patient core HBV antibody positive at screening will be listed.

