4.7.5 Vital Signs

Vital sign and physical examination results, and ECG data will be included in individual patient listings.

Changes from study baseline in vital signs will be summarized by visit and group. Changes from pre-infusion baseline to post-infusion timepoints will also be summarized for each infusion.

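### SAP 4.5 sets baseline by the date of first infusion with no pre-dose condition; read literally, the study baseline for the by-visit vital-sign summary is a post-infusion reading

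*SAP*

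**What the plan says.** SAP 4.5 gives a single rule. "Apart from EDSS, for all other assessments", it says, "the baseline value will be used as the last non-missing value on or before the date of the first infusion of study drug". It mentions neither clock time nor a pre-dose condition. The sentence sits under Efficacy Analysis, but SAP 4.7 (Safety Analyses) supplies no baseline definition of its own.

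SAP 4.7.5 then plans two vital-sign summaries. The first is by visit: "Changes from study baseline in vital signs will be summarized by visit and group". The second is by infusion, and its stated reference is a pre-infusion baseline.

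Protocol Table 1, footnote c (repeated in section 5.12.1) sets the readings on infusion days. "On infusion visits, the vital signs should be taken within 45 minutes prior to the methylprednisolone infusion in all participants". A further reading is due before study drug, then one every 15 minutes for the first hour, then one every 30 minutes "until 1 hour after the end of the infusion".

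The SAP's amendment rationale explains why the rule is date-based. Version 3 lists a "Change of the baseline definition for assessments other than EDSS to include the baseline/Day 1 visit into the baseline", because many Day 1 assessments were dated after the day of randomization.

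For the open-label extension (OLE), SAP 4.4 takes the latest score up to and including the first OLE dose, again without saying whether the value must precede that dose.

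**The concern.** A study baseline should be unaffected by randomized treatment. A rule that accepts anything recorded on the infusion date does not secure this for a measure read many times that day, before, during and after the infusion. If an analyst programs the rule as written, the reference value for every later visit is one taken after the first infusion.

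The reference could then differ between arms for a reason that is itself a treatment effect. Protocol 2.1.4.1 reports first-infusion reactions in 30% to 43.6% of ocrelizumab-treated patients in the Phase II relapsing-remitting study, with tachycardia, flushing and pyrexia among the common symptoms. Section 7.3.1.1 lists hypotension as a reaction symptom. A first-day effect on pulse, temperature or blood pressure would enter every later change from study baseline with its sign reversed.

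**Working it through.** The plan states no figure for this point, so the check applies the SAP 4.5 rule to the Day 1 schedule.

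**Inputs**
- Reading times: Protocol Table 1, footnote c.
- Infusion length: about 150 minutes for the 300 mg ocrelizumab or placebo infusion (Protocol 6.2.1.3, Table 7).
- Baseline rule: SAP 4.5.

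**Step 1. List the readings on the date of first infusion.**
- Before dosing: one within 45 minutes before methylprednisolone and one before study drug. That is 2.
- After the start of infusion: 15, 30, 45 and 60 minutes, then 90, 120, 150, 180 and 210 minutes. That is 4 + 5 = 9.
- Total: 2 + 9 = 11.

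**Step 2. Apply the rule.** The last non-missing value on that date is the 210-minute reading, and 210 - 150 = 60 minutes after the infusion ends. With the ±10-minute tolerance it falls between 200 and 220 minutes, that is 50 to 70 minutes after the end. If that reading is missing, the rule falls back to the one before it. It reaches a pre-dose value only if all 9 later readings are missing. If reading times were not recorded, the rule does not determine which of the 11 is last.

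**Step 3. Effect on a later change.** Let P be the pre-dose value, P + d the post-infusion value and V the value at a later visit.
- Intended change: V - P.
- Literal change: V - (P + d) = (V - P) - d.
- Bias: -d at every later visit.

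The documents give no value of d. In assumed units of the measure:

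| Assumed d | Bias in each later change |
|---|---|
| -10 | +10 |
| -5 | +5 |
| 0 | 0 |
| +5 | -5 |

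**Step 4. Effect on the comparison of arms.** With mean shifts d_O (ocrelizumab) and d_P (placebo), the difference in mean change is biased by -(d_O - d_P). A shift common to both arms cancels in the comparison but still biases each arm's own summary by its -d.

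**Step 5. Which analyses use this baseline.**
- By-visit vital-sign change (SAP 4.7.5): exposed, since no other study baseline is defined.
- Per-infusion vital-sign change (SAP 4.7.5): not exposed, since it names a pre-infusion reference.
- EDSS endpoints: not exposed; SAP 4.5.1 gives EDSS its own baseline.
- MRI: the baseline scan is due at least 10 days before the baseline visit (Protocol 5.11.2).
- Patient-reported outcomes: completed before study drug (Protocol 5.20).
- 25-foot walk, as part of MSFCS: Table 1 schedules one collection at the baseline visit, with no repeat after dosing.

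**The case against.** **Scope.** The rule sits in the efficacy section, so *all other assessments* may mean all other efficacy assessments. That reading is possible. It leaves study baseline in SAP 4.7.5 with no definition at all, and the same clause is needed.

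**Intent.** Version 3 set out to bring the Day 1 visit into the baseline, and nothing suggests post-dose values were wanted. This stands. The point concerns what the wording selects, and a competent programmer may well have added a pre-dose filter. The documents do not say.

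**Impact.** The summary aimed at acute infusion effects is the per-infusion one, and it is sound. The Phase II percentages are adverse-event incidences, not shifts in pulse or blood pressure an hour after infusion. The same section of the protocol reports no unanticipated, clinically significant vital-sign abnormalities associated with ocrelizumab. This also stands: the direction of the bias follows from the algebra, but its size is unknown and could be small.

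**Stronger readings that the documents do not support.** A reader might infer that the CD19 baseline is also post-dose, so that B-cell depletion would be understated, because Protocol 5.10.1.1 says B-cell samples at the baseline visit are "taken before and after dosing" and SAP 4.7.4 reports percent change from baseline. Table 1, footnote r requires cell-sorting samples before infusion on infusion days. Table 1 has one such mark at baseline, with the next at Week 2. Protocol 7.3.1.1 calls 14 days the first timepoint of assessment. Only pharmacokinetic samples have a specified post-infusion draw (footnote m; section 5.14.1). A Day 1 post-dose CD19 count is therefore not shown to exist, and any figure for its effect would rest on assumed depletion. Nor do the documents support an inference that efficacy baselines are contaminated, for the reasons in step 5 of the working.

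**Conclusion.** The concern holds for one analysis. Under the rule as written, the study baseline for the by-visit vital-sign summary is a reading about 60 minutes after the first infusion in every dosed patient with complete, timed readings. It can differ by arm, and each later change is biased by -d, with d unknown.

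This rests on three assumptions: the SAP 4.5 rule governs safety data, since no other definition is offered; the infusion takes about 150 minutes; and the scheduled readings were recorded with times.

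The affected output is a descriptive safety table. The primary result does not depend on it, and no secondary efficacy endpoint is shown to be affected. The point is still live: SAP 2.3 lists the final study report as planned, and SAP 4.7.6 repeats the vital-sign summaries for the extended controlled and OLE periods. Protocol Table 4, footnote g requires the same serial readings at OLE infusions, where former placebo patients receive their first ocrelizumab. The OLE rule is worded for scores such as EDSS and MRI, so the gap there arises only if it is also applied to vital signs.

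**What to change.** - In SAP 4.5, define baseline for assessments other than EDSS as the last non-missing value before the start of the first study-drug infusion, by date and time. Where time is missing, use the record labelled pre-dose.
- State that this definition also serves as study baseline in SAP 4.7.
- Name one pre-dose vital-sign reading, because footnote c requires two and a bare *before infusion* would pick the second. The pre-methylprednisolone reading would also exclude any effect of premedication.
- Use the same pre-dose wording wherever the OLE baseline is applied to vital signs.
- Record how the vital-sign baseline was derived for the completed primary report, so that a reader can tell whether the tables are comparable.

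The cost is a sentence or two in the SAP and a filter in the analysis datasets. A few baselines will be missing where neither a time nor a pre-dose label was recorded.

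Separately, Protocol 5.10.1.1 and Table 1, footnote r should be reconciled on when B-cell samples are drawn at the baseline visit.
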